The PACE study (AHRQ K12HS023011) compared weight loss programs that started either before knee replacement (PACE) or started 12 weeks after surgery (Delayed PACE). Sixteen patients were randomized (63.3±7.5 years old, 69% female, 69% White, BMI of $36.5 \pm 5.1 \text{ kg/m}^2$) to PACE or Delayed PACE. Primary outcomes from 11 participants were objectively assessed at 26 weeks after surgery. Nine participants provided self-reported outcomes at approximately 12.78±1.5 months after knee replacement. Participants in Delayed PACE lost significantly more weight (-7.6±5.9kg, -7.9±5.9%) than PACE (-2.5±2.7kg, -2.6±2.6%) at 26 weeks ($P=0.03$). Delayed PACE maintained greater weight loss outcomes than participants in PACE at one year post-operatively. Pain intensity decreased ($P<0.001$) and function improved ($P=0.001$) significantly, but no significant changes were observed in physical activity (Table 1).

Table 1. Physical Activity Pre- and Post-Surgery in PACE (n=6) & Delayed PACE (n=7)

	Baseline	12 Weeks	26 Weeks
Bouted MVPA, min/week			
PACE	81.2±141.8	3.5±5.4	33.3±76.4
Delayed PACE	37.6±85.7	62.1±135.8	78.1±108.0
Steps/day			
PACE	5715.7±3098.0	4255.6±1687.8	4991.8±2910.2
Delayed PACE	6062.4±2817.6	4943.6±1653.2	6324.4±2201.3

The research team has experience with recruitment of TKR patients in the Columbia, SC area. Currently, we have recruited 12 patients who underwent a TKR to participate in an ongoing study examining the use of Fitbits and social support on physical activity over a 4-month period. To date, 73% of patients recruited for this study are from the Columbia, SC region. Additionally, across the 5 orthopedic surgeons within the Palmetto Health USC Orthopedic Center, an average of 21.8 TKR are completed each week.

3) Objectives / Research Aims

The purpose of this proposed project is to conduct a pilot randomized controlled trial to examine the feasibility and preliminary efficacy of a physical therapist led physical activity intervention on physical activity levels in TKR patients after surgery. The specific aims of the project are:

Aim 1: To examine the feasibility and acceptability of conducting a randomized controlled trial examining a physical therapist led physical activity intervention for TKR patients within an outpatient physical therapy facility. Specifically, enrollment, retention, session attendance and duration, treatment fidelity, and patient and physical therapist satisfaction will be examined.

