identified by Palmetto Health Physical Therapists will be provided information about the study verbally by a USC research staff member. Interested patients will be able to ask questions and read the consent form. They will have the opportunity to complete the informed consent process either at the first or second outpatient physical therapy appointment.

b. Inclusion and Exclusion Criteria

After initial identification of potential patient participants by physical therapists, research staff will screen patients for eligibility criteria in-person or over the telephone.

Inclusion criteria:

Eligible participants will 1) be 40-79 years of age, 2) have had a knee replacement in the last 2 months, 3) be willing to wear an accelerometer for 7 days during assessments, and 4) be English speaking.

Exclusion criteria:

As all patients will be under physicians' supervision post-TKR, participants will only be excluded if they (1) have any contraindications to activity, (2) have a mobility limiting comorbidity (e.g. spinal stenosis), or (3) have a scheduled surgery (i.e., TKR on contralateral knee) within the next 6 months.

c. Local Number of Subjects

We will aim to randomize 50 patients that had a knee replacement within the last 2 months and are attending outpatient physical therapy at the Palmetto Health USC Orthopedic Center. We anticipate that we will need to approach and screen approximately 75 patients to enroll our goal of 50 patients.

d. Study-Wide Number of Subjects

NA

e. Study Timelines

Subject participation will last 12 weeks. We estimate it will take 15 months to complete the study, which will include finished study enrollment, data collection and data analysis (See Figure 1).

Figure 1. Project Timeline

	Project Month														
	1	2	3	4	5	6	7	8	9	10	11	12	13	14	15
Finalize protocol & IRB approval	X	X	X												
Recruit TKA patients (n=50)				X	X	X	X	X	X	X	X	X	X		
Intervention				X	X	X	X	X	X	X	X	X	X		
Completing 12 week assessments				X	X	X	X	X	X	X	X	X	X	X	
Data Analysis														X	X
Prepare manuscript & presentations														X	X
Draft & submit NIH R21 or R01														X	X

f. Study Endpoints

[figure not shown]

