Assessments will be completed before the second outpatient therapy session (baseline) and at 12 weeks after TKR. Detailed descriptions and a timeline of outcomes are provided below in the text and Table 2. Briefly, at both assessments, participants will be asked to complete surveys (demographics, brief medical history, KOOS, PROMIS, self-identification), which should take approximately 20 minutes to complete. Based on participant preferences, surveys will be able to be completed on paper or online via RedCAP, with the exception of the PROMIS surveys which are computer adaptive surveys. Participants will also be given an Actigraph Link accelerometer and ActivPAL monitor to wear for 7 days at each assessment. These monitors will be provided at the in-person assessment or mailed to the participants. At the end of the 7 days, these monitors will be returned to the PT clinic or participants will be provided with a prepaid padded envelope to return the monitor. Only at 12 weeks will participants complete functional tests and the Surgery and Medication Questionnaire, which will take approximately 15 minutes to complete. In the event participants are unable to complete the function tests at the in-person assessment, we will ask participants to complete the chair stand test at home and self-report the outcomes. Participants will not be asked to complete the 6-minute walk or timed up and go at home. Participants will receive \$20 for completing the 12-week assessment.

Measure	Baseline	12 Weeks
Participant Demographics	X	
Participant height and weight	X	X
Brief Medical History	X	X
Knee Injury and Osteoarthritis Outcome Score (KOOS)	X	X
PROMIS Pain Intensity, Pain Interference, & Mobility	X	X
WOMAC Pain and Stiffness	X	X
Physical Function		
6-minute walk		X
Timed up and go		X
Chair stands		X
Physical activity (Actigraph)	X	X
Sedentary time (ActivPAL)	X	X
Self-Reported Exercise Identity	X	X
PATH Study Survey		X

Primary Outcomes: The feasibility and acceptability of conducting a randomized controlled trial within an outpatient physical therapy setting is the primary endpoint. Specifically, we will examine the number of participants enrolled vs. approached, participant retention, number of therapy sessions attended, session duration, and treatment fidelity. Further, participants will complete a PATH Study Survey at the 12 week assessment. Physical therapists will complete a brief evaluation about delivering the PATH program.

Secondary Outcomes:

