- Physical activity will be measured using Actigraph Link accelerometers owned by the TecHealth Center at the University of South Carolina. During assessments, participants will be asked to wear the Actigraph on their waist for 7 days. Non-wear time will be defined as ≥ 90 minutes with zero activity counts, allowing for up to 2 minutes of <100 counts/min.²⁶ Physical activity will be categorized as light (100-2019 counts/min) and moderate-to-vigorous (MVPA) (≥ 2020 counts/min).²⁷ Total MVPA over the week will be calculated. Steps/day will also be obtained. A valid day will be considered if participants wore the accelerometer for at least 10 hours/day. Participants will also be asked to complete a log indicating times the accelerometer was worn and taken off over the 7-day assessment period.
- Sedentary time will be measured using ActivPAL™ (PAL Technologies Ltd, Glasgow, UK), a small lightweight (15 g) uni-axial accelerometer. The time spent sitting/lying, standing, and walking, transitions and step counts will be determined. The ActivPAL summarizes data in 15 second intervals over 24 hours at a sampling frequency of 10 Hz.²⁸ During assessments, participants will be asked to wear the ActivPAL on their thigh for 7 days. Participants will also be asked to complete a log indicating times the ActivPAL was worn and taken off over the 7-day assessment period.
- Physical function measures will include the chair stand, timed up and go, and 6-minute walk test. All physical function tests will be completed following Osteoarthritis Research Society International (OARSI) recommendation procedures.²⁹ During the chair stand test, patients are asked to complete as many chair stand repetitions as possible during a 30-second period. The Timed Up and Go Test assesses the time in seconds taken to rise from a chair, walk 3-meters, turn, walk back to the chair, and sit down. The Six Minute Walk Test evaluates the maximal distance a patient can cover during a 6-minute period.
- Patient-Reported Outcomes will be assessed using two methods: 1) Patient-Reported Outcomes Measurement Information System (PROMIS)³⁰ utilizes a computer adaptive test via RedCap.³¹ We will assess pain intensity, pain interference, and mobility; 2) Western Ontario and McMaster Universities Arthritis Index (WOMAC) is a 15-item survey assessing pain and stiffness over the last 48-hour on a 5-point Likert scale.³²

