Treatment Fidelity. Due to the open, group-like nature of physical therapy and patient confidentiality, we are unable to audio record treatment sessions. Therefore, to monitor treatment fidelity to ensure intended session content for both conditions is delivered and that unintended session content (i.e., contamination such as goal setting on physical activity levels with a patient randomized to PATH-12) is not delivered, physical therapists will complete a session checklist. In addition, random observations will occur by USC research staff. The physical therapist and observation fidelity checklists will monitor session duration, goals set, and indication if aerobic physical activity was discussed.

h. Data and Specimen Banking

NA

i. Statistical Analysis

Descriptive statistics will be used to describe baseline characteristics, establish recruitment and retention rates, and examine intervention intensity (session frequency, duration, and fidelity) and patient and therapist satisfaction. Mixed ANOVA or ANCOVAs, if appropriate adjustments are required based on baseline characteristics, will examine the changes in physical activity levels (MVPA/week, steps/day), and pain (PROMIS and WOMAC) across time between PATH and PATH-12. Additionally, differences between PATH and PATH-12 in physical function (chair stands, Timed Up and Go, 6-minute walk) will be examined at 12 weeks. Although the proposed study may not be powered to detect significant differences, the results will allow us to collect feasibility and acceptability data, refine the intervention, if necessary, and determine effect sizes for future grant submissions.

j. Data Management

All surveys will be administered either on paper or online via REDCap (secure, web application for building and managing online surveys and databases – managed by the University of South Carolina). Paper surveys will be stored in a locked filing cabinet at Palmetto Health-USC Orthopedic Center or the TecHealth Center at University of South Carolina. All computer files will be password protected. Only the study team will have access to the data.

k. Confidentiality

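### For the change outcomes the default mixed ANOVA does not adjust for the baseline value; one pre-specified baseline-adjusted analysis would be more precise and safer against dropout that differs by arm

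*Combined protocol and SAP*

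**What the plan says.** Section 7) i (Statistical Analysis) of the combined protocol and SAP names the methods for the change outcomes as "Mixed ANOVA or ANCOVAs". In full, it states: "Mixed ANOVA or ANCOVAs, if appropriate adjustments are required based on baseline characteristics, will examine the changes in physical activity levels", and applies the same methods to PROMIS and WOMAC pain. Mixed ANOVA is therefore the default. ANCOVA is conditional on a trigger that is not defined, its covariates are not named, and the baseline value of the outcome is not promised as one of them.

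Section 7) f (Study Endpoints) sets two visits: "Assessments will be completed before the second outpatient therapy session (baseline) and at 12 weeks after TKR". The function tests are done at 12 weeks only. Their comparison ("Additionally, differences between PATH and PATH-12 in physical function") is a separate 12-week analysis and is not affected by this point.

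The target in section 7) c is "We will aim to randomize 50 patients". Section 7) i concedes limited power ("Although the proposed study may not be powered to detect significant differences") and says that the results will supply effect sizes for later grant applications. The documents give no analysis set for the change outcomes, no missing-data method, no expected dropout and no baseline-to-12-week correlation. For the accelerometer, "A valid day will be considered if participants wore the accelerometer for at least 10 hours/day" defines a valid day, but no minimum number of valid days is set.

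**The concern.** In its usual form, a two-visit mixed ANOVA uses only patients with both values. Its group-by-time test is the two-sample comparison of mean change and ignores how far change can be predicted from the starting value. Two costs follow. Precision is lost in a trial of 50, although the baseline values are collected anyway. And if the patients who leave differ in baseline activity or pain between PATH and PATH-12, the completers' change comparison is shifted. Either problem would pass into the effect sizes used to plan the next trial. Leaving ANCOVA to a judgement about baseline characteristics also means that the model is chosen after the data are seen.

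**Working it through.** The plan has no power calculation, variance or dropout figure to reproduce. The inputs are 50 patients and two visits (from the document), and these assumptions: 25 per arm, 20% missing at 12 weeks, correlation ρ = 0.3, 0.5 or 0.7, equal SD at both visits, clustering ignored.

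**1. Precision.** Per patient, in units of the outcome variance σ²:
- change score: 2σ²(1 − ρ)
- 12-week value adjusted for baseline: σ²(1 − ρ²)
- ratio, adjusted to change: (1 + ρ)/2 = 0.65, 0.75, 0.85 for ρ = 0.3, 0.5, 0.7

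In large samples the variance is thus 35%, 25% and 15% lower. Estimating the slope from about 50 × 0.8 = 40 patients costs a little: simulation gives about 34% to 12% over the same range. At ρ = 0.5 the simulated standard errors are 0.318 SD (change) and 0.279 SD (adjusted), and (0.279/0.318)² = 0.77, or 23% lower variance. As a check, √[2 × 0.5 × (1/20 + 1/20)] = 0.316.

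**2. How much of this is recovered data?** A likelihood model with no constraint on the baseline means, keeping patients seen only at baseline, moves the standard error from 0.318 to 0.310. (0.310/0.318)² = 0.95, about 5% lower variance. Most of the gain is baseline adjustment.

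**3. Bias.** Let δ be the shift in mean baseline among completers. With retention log-odds of 1 per baseline SD and 80% retained, numerical integration gives δ = 0.173 SD. The bias of the change comparison is (ρ − 1) × (δ in PATH − δ in PATH-12).

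| Dropout depends on baseline | ρ = 0.3 | ρ = 0.5 | ρ = 0.7 |
|---|---|---|---|
| Equally in both arms | 0 | 0 | 0 |
| In PATH only: (ρ − 1) × 0.173 | −0.12 | −0.09 | −0.05 |
| In opposite directions: 2(ρ − 1) × 0.173 | −0.24 | −0.17 | −0.10 |

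Simulation with 2,000,000 per arm agrees to within 0.01 SD. In the same scenarios, complete-case ANCOVA on the baseline value and a likelihood model using all observed visits both have bias of about 0.

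**4. Scale, for illustration only.** Pooling Table 1 of the earlier PACE trial (n = 6 and 7) gives step SDs of √[(5 × 3098.0² + 6 × 2817.6²)/11] = 2948 at baseline and √[(5 × 1687.8² + 6 × 1653.2²)/11] = 1669 at 12 weeks. The one-arm case is then (ρ × 1669 − 2948) × 0.173, about −310 to −420 steps/day. PACE's baseline came before surgery and PATH's comes after it, so these SDs may not carry over.

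**5. What adjustment does not cure.** If the treatment effect itself varies with baseline (assumed interaction slope −0.3, ρ = 0.5, same dropout in both arms), all three estimators are biased by about −0.05 SD.

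**The case against.** Several parts of the opposing case stand.

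- A reader might infer that dropout related to baseline biases the comparison by itself. It does not: the first row of the table is zero. The documents make a difference between arms conceivable, since only PATH patients are coached during therapy and only PATH-12 patients are offered a 12-week session meant to aid retention. They do not show that one exists.
- A reader might infer that missing one monitor week removes a patient from the trial's analyses. Any loss would be outcome by outcome: MVPA and steps would be affected, but PROMIS, WOMAC and the 12-week function tests would not. Because no minimum number of valid days is set, the text does not define a failed week either.
- The earlier trial does not forecast dropout here. "Primary outcomes from 11 participants were objectively assessed at 26 weeks after surgery" gives 11/16 = 69%, but that was a weight-loss trial at 26 weeks. The heading of its activity table shows 6 + 7 = 13 of 16 (81%), and PATH participation lasts 12 weeks.
- ANCOVA is already named, and with the baseline value as covariate it performs well. This narrows the point, but the text promises neither its use nor that covariate.
- Adjustment has a risk of its own. Sites are randomized and patients are identified afterwards, so the arms may differ at baseline. If they differ by an assumed 0.25 SD at both visits with no true effect on change, a model that forces equal baseline means shows a spurious 0.25 × (1 − ρ) = 0.125 SD at ρ = 0.5 or 0.075 SD at ρ = 0.7. ANCOVA has the same expected shift, and the change score shows none. This is a reason for sensitivity analyses and against relying on the constraint alone.

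**Conclusion.** The point holds as a better choice of analysis, with minor to moderate weight. The precision gain does not depend on any dropout pattern: about 12–34% lower variance over the assumed correlations, almost all of it from baseline adjustment. The bias of 0.05–0.12 SD is conditional on dropout that depends on baseline in one arm only, and should be reported as a vulnerability and not as a demonstrated defect. That the mixed ANOVA is restricted to completers is inferred from the usual form of the method; the plan does not say so. Feasibility is the primary endpoint and limited power is admitted, which caps the importance. What keeps the point alive is the intended use of these effect sizes.

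**What to change.** In section 7) i, replace the mixed ANOVA or conditional ANCOVA with one pre-specified analysis of each 12-week value for MVPA/week, steps/day, PROMIS and WOMAC. It should always adjust for the baseline value of that outcome and include phase and site. It may be fitted by REML as a mixed model to all observed baseline and 12-week values, so that patients with one visit are kept. It should not rest on an equal-baseline-mean constraint alone. State the analysis set and the minimum number of valid monitor days. As sensitivity analyses, report an all-available-data mixed model without the constraint and the completers-only change comparison.

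The cost is a few sentences of plan text and slightly more modelling with standard software; no new data are needed. Adjusted and change-score results may disagree if the arms are imbalanced at baseline, so the plan should say in advance which one leads.

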- Self-reported exercise identity will be assessed at baseline and 12-week assessments using the Self-Reported Exercise Identity Scale.³³ Participants will rate on a scale from 1 (strongly disagree) to 5 (strongly agree) their feelings relating to exercise identity. Examples include, “I would feel a real loss if I were forced to give up exercising” and “I need exercise to feel good about myself.”

g. Procedures Involved

Design Overview: We propose to conduct a pilot two-arm cluster randomized controlled trial with patients attending outpatient physical therapy following TKR. The proposed project was developed in collaboration with [name], Senior Physical Therapist at Palmetto Health USC Orthopedic Center. Over 9 months, TKR patients (n=50) attending outpatient physical therapy at Palmetto Health USC Orthopedic Center will be recruited and randomized to either 1) PATH-12 (control), or 2) PATH. Due to potential contamination of the intervention between patients in PATH-12 and PATH during typical open, group-like physical therapy settings, we have opted to randomize physical therapy sites instead of individual patients. Specifically, physical therapy sites will be randomized to either Immediate or Delayed. The first phase of the study will take place starting in November and end after 25 participants have been recruited. During this time, those sites randomized to Immediate will receive the PATH intervention and those sites randomized to Delayed will receive the PATH-12 intervention. There will then be a “wash out period” to allow for all the participants to finish their current PT. After this “wash out period”, the second phase of the study will begin and will end after 25 participants have been recruited. During this time, those sites randomized to Immediate will receive the PATH-12 intervention and those sites randomized to Delayed will receive the PATH intervention.”

Screening: Participants will be required to complete a brief screening after the first physical therapy appointment. Research staff will administer the screening in-person or over the telephone. The screening will assess eligibility criteria and willingness to participate. Following the completion of the screener, eligible and interested participants will be invited to complete the informed consent process.

Randomized Conditions:

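### Sites are randomised and swap condition between two phases, but the Aim 2 analysis has no site or phase term, so unequal recruitment can turn a phase difference into an apparent PATH effect

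*Combined protocol and SAP*

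**What the plan says.** Section 7g (Design Overview) describes a cluster-randomised pilot. To avoid contamination, "we have opted to randomize physical therapy sites instead of individual patients". Sites are allocated to Immediate or Delayed. On timing: "The first phase of the study will take place starting in November and end after 25 participants have been recruited". In that phase Immediate sites deliver PATH and Delayed sites deliver PATH-12. A wash-out follows "to allow for all the participants to finish their current PT", and the sites then swap condition for a second phase, which also ends at 25 recruits. No target per site or site group is set, and the number of sites is not given.

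Section 7i plans a mixed ANOVA, or an ANCOVA if baseline characteristics call for adjustment. These "will examine the changes in physical activity levels (MVPA/week, steps/day), and pain (PROMIS and WOMAC) across time between PATH and PATH-12". In addition, "differences between PATH and PATH-12 in physical function (chair stands, Timed Up and Go, 6-minute walk) will be examined at 12 weeks". Time here means baseline and 12 weeks, not study phase. No site, cluster, sequence or phase term is named anywhere.

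Section 7f adds a point that matters here: "Only at 12 weeks will participants complete functional tests". Section 7i says the results will be used to "determine effect sizes for future grant submissions".

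**The concern.** In this design condition is fixed by site group and phase together: PATH patients are the Immediate sites' phase 1 recruits plus the Delayed sites' phase 2 recruits. A comparison that ignores phase is protected only if both arms draw equally on the two phases. Nothing in the plan ensures that, and section 5 allows therapists to be added if recruitment is slow, so site shares can move. When the split is the same in both phases, each arm still totals 25, so equal arm sizes would not reveal the problem.

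Exposure differs by outcome:

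- **Chair stands, Timed Up and Go, 6-minute walk.** There is no baseline, so any phase difference in level enters the comparison. The documents name no cause for one.
- **MVPA, steps, pain.** A level shared by both visits cancels in the change, so only a phase difference in change matters. For MVPA and steps, season is a possible source: phase 1 starts in November and section 7g gives 9 months of recruitment, so the phases fall in different months.

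At stake is the size of the Aim 2 estimate more than a significance claim, since section 7i already concedes limited power.

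**Working it through.** **Plan's own figure.** The target of 50 is 25 + 25. No alpha, power, effect size or SD accompanies it, so there is no sample size calculation to reproduce.

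**1. Share of a phase difference that enters the PATH effect.** Let n be the recruits by site group (I, D) and phase (1, 2). The share is the proportion of PATH patients from phase 1 minus that of PATH-12 patients: nI1/(nI1+nD2) − nD1/(nD1+nI2).

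| I:D, phase 1 then phase 2 | Calculation | Share |
|---|---|---|
| equal in both | – | 0 |
| 15:10, 15:10 | 15/25 − 10/25 | 0.20 |
| 18:7, 18:7 | 18/25 − 7/25 | 0.44 |
| 18:7, 13:12 | 18/30 − 7/20 | 0.25 |
| 18:7, 7:18 | 18/36 − 7/14 | 0 |

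The direction of the bias depends on which group recruits more.

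**2. Bias.** Assume a phase difference of 0.25 to 0.5 SD.

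- At 15:10: 0.20 × 0.25 = 0.05 SD to 0.20 × 0.5 = 0.10 SD.
- At 18:7: 0.44 × 0.25 = 0.11 SD to 0.44 × 0.5 = 0.22 SD.

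For scale in steps, Table 1 (Preliminary Studies) gives 12-week SDs of 1,687.8 (n=6) and 1,653.2 (n=7). Pooled: √((5 × 1687.8² + 6 × 1653.2²)/11) = 1,669 steps/day. The bias is then 83 to 167 steps/day at 15:10 and 184 to 367 at 18:7. With 13 patients this shows order of size only.

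**3. Precision.** With 25 per arm the 95% CI half-width is about 0.56 to 0.58 SD for the function tests, or 0.62 with the terms at 18:7. For change outcomes it is about 0.5 SD, assuming a baseline to 12-week correlation of 0.6.

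**4. Type I error.** Simulated with 40,000 trials per setting, 50 patients, no PATH effect, no carry-over and the same split in both phases. Entries are without → with site and phase terms.

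| Setting | 13:12 | 15:10 | 18:7, 0.25 SD | 18:7, 0.5 SD |
|---|---|---|---|---|
| Function, 4 sites, ICC 0.05 | 4–6% → 5–7% | 5–7% → 5–7% | 6–8% → 5–6% | 10.5–12.7% → 5.1–6.4% |
| Change, 4 sites, ICC 0.05 | – | 5–7% → 5–8% | 7–9% → 5–7% | 12–15% → 5–7% |

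Ranges cover site effects that are wholly stable or half site-by-phase. With two sites, ICC 0.10 and half of it site-by-phase, both phase differences together:

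| Setting | 13:12 | 15:10 | 18:7 |
|---|---|---|---|
| Function | 11–12% → 13% | 12% → 12–13% | 15–19% → 11% |
| Change | 12–13% → 15% | 14% → 14–15% | 17–22% → 13% |

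With the terms, bias was about 0 throughout.

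**5. Form of the terms.** For noise-free cell means at 18:7 with a 0.5 SD phase difference in change, the condition-by-time estimate is 0.22 with no terms, 0.22 with site and phase main effects only, and 0 with site-by-time and phase-by-time.

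**6. Carry-over.** Suppose phase 2 PATH-12 patients at Immediate sites receive a fraction c of the PATH effect, and p is the Immediate share. The planned comparison returns 1 − cp of the effect; the model with the terms returns 1 − c/2. At c = 0.5 these are 0.74, 0.70 and 0.64 at 13:12, 15:10 and 18:7, against 0.75. The terms do not remove carry-over.

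**The case against.** The best counter-argument is that, for the accuracy of an estimate, removing bias costs variance. For the function tests (4 sites, ICC 0.05, stable), the terms lower root mean squared error only if the phase difference exceeds about 0.28 SD at 15:10 or 0.31 SD at 18:7. With no phase difference, error rises from 0.276 to 0.281 and 0.307 respectively. Phase differences of that size are assumed, not documented, and several months of recruitment per phase partly average out season. Harm also needs imbalance in a consistent direction: at 15:10 or closer with four sites, type I error is near nominal without the terms. With two sites, which the documents do not rule out, the terms plus baseline move type I error for change outcomes at 13:12 from 12–13% to 17%. Finally, the outcomes are secondary in a pilot.

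All of this stands as a limit on the size of the problem. It does not justify ignoring the randomised unit and the phase on which condition depends. The loss when there is no phase difference is small near balance, and under clear imbalance with a real phase difference the terms remove a bias that would pass into the next trial's planning. The two-site case calls for descriptive reporting, not for leaving the terms out.

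**Conclusion.** The concern holds. The stated analysis does not match the design, and that omission is certain. When one site group recruits more in both phases and the phases differ, the Aim 2 estimate is biased by 20% (15:10) to 44% (18:7) of the phase difference. For an assumed 0.25 to 0.5 SD difference this is 0.05 to 0.22 SD, less than half the CI half-width even at the top of that range. Clear inflation of type I error with four sites appears mainly at 18:7 with 0.5 SD.

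The split, phase difference, ICC, number of sites and baseline correlation are all assumptions. Feasibility is untouched. The point should be fixed because the estimates are intended for future grant applications and the remedy is cheap.

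**What to change.** Keep both sentences in section 7i and the outcomes they name, and add:

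> All PATH versus PATH-12 comparisons of these outcomes will include site and phase as fixed terms, and the baseline value where it is measured; the condition effect will be reported with a 95% CI.

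If the change analysis is kept as a mixed ANOVA, enter the terms as site-by-time and phase-by-time; main effects alone change nothing.

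Also:

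- State the number of sites and report recruitment by site and phase.
- State that the terms remove phase bias and stable site differences, but not site-by-phase variation or carry-over from Immediate-site therapists who delivered PATH in phase 1.
- Report the section 7g fidelity checklist, which covers "contamination such as goal setting on physical activity levels with a patient randomized to PATH-12", by site group and phase, so that carry-over can be seen.
- With two sites, call the between-arm estimate and its CI descriptive.

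**Cost.** Site and phase are known for every participant, so this is a wording change. The terms multiply the variance by 1/(1 − (2p − 1)²): 1.00 at 50:50, 1.04 at 15:10, 1.24 at 18:7. That assumes the same split in both phases and every site recruiting in both. In a four-site example at 15:10 where two sites recruit in one phase only, the variance factor rises from 0.083 to 0.123.

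Root mean squared error without → with the terms (4 sites, ICC 0.05, stable):

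| Outcome, phase difference | 15:10 | 18:7 |
|---|---|---|
| Function, 0.25 SD | 0.280 → 0.282 | 0.297 → 0.307 |
| Function, 0.5 SD | 0.292 → 0.281 | 0.353 → 0.307 |
| Change, 0.25 SD | 0.253 → 0.253 | 0.273 → 0.275 |
| Change, 0.25 SD, baseline also added | 0.253 → 0.228 | 0.273 → 0.249 |

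The gain in the last row comes from the baseline value (correlation 0.6 assumed), not from site and phase.
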